1 INTRODUCTION

Why?

We would like to perform an analysis of the relationship between systemic pH and cardiac function and clinical outcome in critically ill patients in patients hospitalized the Intensive Care Unit.

How is it of relevance and importance to patients and public?

Studying this subject we could provide important information about the impact of systemic pH on cardiac function and clinical outcome in seriously ill patients and enable the clinician to

Full title of the research: **The impact of systemic pH on cardiac function and clinical outcome in the critically ill patient.**

IRAS Project ID: **227870**

understand the best treatment of these patients. Patients will be studied who had cardiac monitoring during their ICU admission and an acid-base metabolic disorder. We exclude those patients with cardiac history or who presented an acute coronary syndrome during ICU admission.

IT IS NOT A THERAPEUTIC STUDY. ONLY OBSERVATIONAL. NO INTERVENTIONS.

Where?

In seven different ICU's between King's College NHS Foundation Hospital and Lewisham and Greenwich NHS Trust

How?

The study will take approximately six month to collect prospectively data from each unit. The data will be extracted from the medical notes and ICU charts. No active involvement with participants.

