2 BACKGROUND AND RATIONALE

3 OBJECTIVES

Goals

Primary

1. Assess whether there are significant changes in cardiac function associated with changes in blood pH.
2. Relate the changes in cardiac function to presence or absence of underlying cardiac disease.

Secondary

3. To establish which factors affected by blood pH have an impact on cardiac function.

Full title of the research: **The impact of systemic pH on cardiac function and clinical outcome in the critically ill patient.**

IRAS Project ID: **227870**

4. Study the mortality of patients admitted to the Intensive Care Unit (ICU) who had continuous cardiac monitoring at any time during their admission and relate it to changes in blood pH.

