4 STUDY DESIGN

- Study population and groups: those patients on haemodynamic monitoring in ICU (PiCCO monitoring)
- **Calculation of the sample size:**

Taking into account that the primary objective of the study is to analyze the relationship between the quantitative variables: change in pH and change in Cardiac Contractility, assuming an alpha risk of 5% (95% confidence level), a 20% beta risk (power of 80%) and a minimum ratio that has an estimated clinical significance with a correlation coefficient of 1.5, a bilateral estimate of sample size of 346 subjects is obtained. Assuming a 5% loss (17 individuals) during the study a total of 363 cases would be necessary.

- **Statistical methods:**

The description of quantitative variables is carried out with central tendency and dispersion indices, whether based on values (mean and standard deviation) or on ordinations (median and interquartile range) according to whether they meet normality or not, respectively. Its graphic representation is done with Histograms and Cash Diagrams. The description of categorical variables is performed with absolute and relative frequencies in percentages. Its graphic representation is done with bar charts.

Full title of the research: **The impact of systemic pH on cardiac function and clinical outcome in the critically ill patient.**

IRAS Project ID: **227870**

The relationship between categorical variables is analyzed by comparing proportions with the Pearson Chi-square test, provided that there are less than 20% of squares in the contingency table with expected frequencies less than 5. In the case that there is more 20% of squares with expected frequencies less than 5, the Fisher's exact test is used bilaterally.

The magnitude of the effect of the relationship between two binary variables has been analyzed with the Ratios of proportions or Relative Risk and with the Odds Ratio.

The relationship between a binary exposure variable and a quantitative response is analyzed with the Student-Fisher t test for independent samples if the normality condition is met. According to whether or not the equality of variances are met, the Student-Fisher t test is used for independent groups for homogeneous variances or for non-homogeneous variances, respectively. In case of not fulfilling the condition of normality, the comparison of two means is made with the non-parametric Mann-Whitney U test.

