20 ARCHIVING

Date of birth	
Sex (M/F)	
Hospital ADMISSION date	
ICU ADMISSION date	

 • Unplanned/emergency admission. • Planned /elective admission. 	
ICU DISCHARGE date	
Discharged alive from ICU?	(Y / N)

 • From ICU to home directly. • From ICU to hospital ward. • From ICU to another ICU (other hospital) 	
Discharged alive from HOSPITAL?	(Y / N)

 • Home • Nursing home or equivalent 	
28-day mortality. Death occurring within 28 days of hospital discharge?	(Y / N)
Admitting diagnosis group:	

 • Cardiac arrest/ other causes of cardiogenic shock • Cardiothoracic surgery • Septic shock 
 ➢ Medical ➢ Neutropenic sepsis/ other haematology & oncology sepsis ➢ Surgical • Post-operative management: any other speciality 	

 • Haemorrhagic shock 
 ➢ Major trauma ➢ Gastrointestinal/other medical ➢ Post-surgical • Acute respiratory failure 
 ➢ COPD /asthma exacerbation ➢ Pneumonia ➢ Other causes • Acute renal failure requiring hemofiltration • Trauma/neuro-surgical • Decompensated liver disease/ acute liver failure • Diabetic ketoacidosis/hyperosmotic syndrome • Others 	

PATIENT RESEARCH ENCRYPTED CODE:
	

Chronic diseases
 
 • Ischaemic heart disease. • Congestive heart failure • Atrial fibrillation/Atrial flutter • Devices 
 ➢ Pacemaker (PM) +/- Implantable cardioverter-defibrillator (ICD) ➢ Cardiac resynchronization therapy (CRT) +/- (ICD) • Arterial hypertension • Pulmonary hypertension • Pulmonary embolus/deep vein thrombosis • COPD/Asthma • Fibrosis • Diabetes mellitus • End stage kidney disease (on regular dialysis) • Chronic kidney disease or pre-dialysis (NOT on dialysis) • Liver disease • Morbid obesity. • Recent quimiotherapy / radiotherapy (last 30 days) • Haematology malignancies 
 ➢ Acute myeloid leukaemia (AML) ➢ Chronic lymphocytic leukaemia (CLL) ➢ Myeloma ➢ Lymphoma • Other hemato-onco malignancies 	

Severity scores
 
 • APACHE II 	

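### The form's chronic-disease list has no item for heart disease beyond a few named conditions and shows no not-recorded code, so it cannot fully support the cardiac-disease grouping in primary goal 2

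*Combined protocol and SAP*

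**What the plan says.** Section 3 (Objectives) sets the second primary goal: "Relate the changes in cardiac function to presence or absence of underlying cardiac disease". No section says which recorded items make up that variable. Section 8 gives general rules for a binary exposure and a quantitative response (t test or Mann-Whitney), without naming the exposure.

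The data form is printed under section 20 (Archiving). The cardiac entries in its chronic-disease block begin "Ischaemic heart disease. • Congestive heart failure • Atrial fibrillation/Atrial flutter" and continue with implanted devices and arterial and pulmonary hypertension. The block ends at the heading for severity scores, so the list itself appears complete. It has no residual cardiac item. Elsewhere the form does use catch-alls: "Other hemato-onco malignancies" in the same block, and a final residual entry in the list of admitting diagnoses.

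That admission list also contains "Cardiac arrest/ other causes of cardiogenic shock" and cardiothoracic surgery. No rule relates these groups to goal 2. The discharge and mortality rows print a yes/no code; the disease items, as shown, print none. Section 1 gives the source: "The data will be extracted from the medical notes and ICU charts".

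Section 1 also says that patients with a cardiac history, or with an acute coronary syndrome during the ICU stay, are excluded. Sections 7.1 and 7.2 contain no such criterion.

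**The concern.** A primary goal rests on a grouping that the form can support only in part. A patient with cardiomyopathy without recorded heart failure, a stenotic or replaced valve, a repaired congenital lesion or earlier cardiac surgery may have nothing to mark. Because the data come from notes, a blank may mean either no disease or no documentation. Neither gap can be closed at analysis, since the information was never collected.

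If such patients are then counted as free of cardiac disease, the comparison group is mixed and the disease group is smaller than it should be. The goal 2 result would be biased, and a reader could not tell how far it reflects the heart's response to pH and how far the form.

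**Working it through.** **1. The plan's own figure.** Section 4 uses a two-sided 5% level, 80% power and "a correlation coefficient of 1.5, a bilateral estimate of sample size of 346 subjects is obtained". A correlation cannot be 1.5. With r = 0.15, the Fisher z formula gives

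n = [(1.960 + 0.842) / atanh(0.15)]² + 3 = 346.6,

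which matches 346. For losses, 346 × 0.05 = 17.3 and 346 + 17 = 363, as stated: "Assuming a 5% loss (17 individuals) during the study a total of 363 cases would be necessary". This calculation serves the correlation of change in pH with change in contractility. It does not cover goal 2, so there is no planned power for goal 2 to reproduce.

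**2. Model for missed heart disease.** The documents give neither input, so both are assumptions: p, the true prevalence of underlying cardiac disease, and Se, the share of those patients whom the form identifies. It is also assumed that nobody is wrongly marked as diseased, that unmarked patients are analysed as disease-free, and that missed patients respond like detected ones. Then

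- diseased share of the comparison group: c = p(1 − Se) / (1 − p·Se)
- observed / true contrast: 1 − c = (1 − p) / (1 − p·Se)
- noncentrality ratio: (1 − c) × √[q(1 − q) / (p(1 − p))], with q = p·Se
- power: Φ(2.80 × ratio − 1.96), where 2.80 is the value for 80% power under correct grouping.

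**3. Worked case, p = 0.30, N = 346.** There are 346 × 0.30 = 103.8 diseased patients.

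- Se = 0.80: 83.0 identified, 20.8 missed, comparison group 263.0. So c = 20.8/263.0 = 0.079, ratio = 0.921 × √(0.1824/0.21) = 0.858, power = 67%.
- Se = 0.70: 72.7 identified, 31.1 missed, comparison group 273.3. So c = 31.1/273.3 = 0.114, ratio = 0.886 × √(0.1659/0.21) = 0.788, power = 60%.

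**4. Range.**

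| p | Se | c | observed/true | power |
|---|---|---|---|---|
| 0.1 | 0.9 | 0.011 | 0.99 | 75.3% |
| 0.1 | 0.8 | 0.022 | 0.98 | 69.8% |
| 0.1 | 0.6 | 0.043 | 0.96 | 56.5% |
| 0.3 | 0.9 | 0.041 | 0.96 | 74.0% |
| 0.3 | 0.8 | 0.079 | 0.92 | 67.2% |
| 0.3 | 0.6 | 0.146 | 0.85 | 51.8% |
| 0.5 | 0.9 | 0.091 | 0.91 | 71.7% |
| 0.5 | 0.8 | 0.167 | 0.83 | 62.8% |
| 0.5 | 0.6 | 0.286 | 0.71 | 45.0% |

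**5. Is the direction fixed?** Let missed patients have k times the effect seen in detected ones. The observed/true ratio is then (1 − c·k) / [Se + (1 − Se)k]. At p = 0.3 and Se = 0.8:

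- k = 2: 0.70
- k = 1: 0.92
- k = 0.5: 1.07
- k = 0: 1.25

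If missed patients respond half as strongly or not at all, the contrast is overstated. Shrinkage depends on the equal-response assumption.

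**6. Limit of the model.** These figures concern a difference in means between two groups. If goal 2 is read as asking whether the effect of pH differs by cardiac disease, they are only a rough guide.

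**The case against.** The strongest case on the other side has six parts.

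- *Placement of unmarked patients.* A reader might infer that the plan puts every unmarked patient among the disease-free. No section says so, because there is no derivation rule. What the documents support is an undefined variable plus a missing item. This objection stands.
- *Acute cardiac admissions.* A reader might also infer that the form loses these. It does not: admitting diagnosis and chronic disease sit on the same form and can be combined. Only a rule is missing, and no section says whether an acute event counts as underlying disease. This stands.
- *The form as shown.* It stops at a severity score and has no fields for pH or cardiac output, so it is visibly partial, and response codes may have been lost in extraction. The absence of a not-recorded code is therefore less certain than the absence of a residual cardiac item, because the chronic-disease block is closed by the next heading.
- *Who is affected.* Section 7.2 excludes arrhythmia, valve insufficiency and intracardiac shunt, section 7.1 sets an upper age of 65, and some cardiomyopathy would be recorded as heart failure. Fewer patients are affected, but not none.
- *Direction of error.* Counting hypertension as cardiac disease could misclassify patients in the opposite direction. This stands.
- *The introduction's exclusion.* If patients with a cardiac history are excluded, goal 2 has almost no disease group, and unlisted heart disease becomes an eligibility failure. This contradiction comes first. It does not remove the need for the item, since a cohort said to be free of cardiac history needs that history recorded to show it.

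**Conclusion.** The point holds in a limited form. The chronic-disease list has no place for heart disease outside its named conditions and, as shown, no code for an undocumented history. A primary goal depends on that information, and it cannot be recovered once data collection is over.

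The effect would be a biased goal 2 contrast, toward zero if missed patients respond like detected ones. The stronger reading, that errors run only one way and the contrast must shrink, is not supported: it needs perfect specificity, equal response in missed patients and a grouping rule that the plan does not contain.

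The fall from 80% to about 60-67% power (p = 30%, Se = 70-80%) is illustrative only. Prevalence, capture and the 80% starting point are all assumed. The correction should be made before data collection, because it costs almost nothing then and cannot be made afterwards.

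**What to change.** 1. First reconcile the exclusion of cardiac history in section 1 with goal 2 in section 3 and with the criteria in sections 7.1 and 7.2. Until that is settled, it is unclear whether goal 2 has a disease group.
2. Add one item to the chronic-disease list: other heart disease (specify).
3. Code each cardiac item yes, no or not recorded.
4. In section 8, name the form items that make up underlying cardiac disease. State whether devices and the two hypertension items count, and how the acute cardiac admission groups are classified.
5. Add a sensitivity analysis for goal 2 that sets apart patients coded not recorded and those whose only cardiac entry is an acute admission group (cardiac arrest or cardiogenic shock, cardiothoracic surgery). This is preferable to dropping them from the main comparison: notes often omit negative histories, so the loss could be large and selective.

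The cost is slightly more form-filling, a few sentences in section 8 and one extra analysis.

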21 PUBLICATION AND DISSEMINATION POLICY

PUBLICATION IN PEER REVIEW JOURNALS

23 APPENDICES

No appendices

Appendix 1: PROTOCOL VERSIONS

Version Stage	Versions No	3rd	Version	Date	Appendix No	detail the reason(s) for the protocol update
			26/03/18
